## 6.3 PATIENT SETS ANALYSED

The following analysis sets will be defined for this trial.

### Screened set

The screened set (SCR) will consist of all patients who were screened for the trial with informed consent given and completed at least one screening procedure at visit 1.

### Randomised set

The randomised set (RS) will consist of all patients in the screened set who were randomised to study drug, regardless of whether any study drug was taken.

### Treated set

The treated set (TS) will consist of all patients who were randomised and treated with at least one dose of the study drug. The assignment of patients to treatment group will be based on the first study drug intake in the double-blind treatment period.

[figure not shown]
### Full analysis set

[figure not shown]
The full analysis set (FAS) will consist of all patients in TS who were treated with at least one dose of the randomised study drug and had a baseline HbA1c assessment. The assignment of patients to treatment groups will be based on the randomised study drug at time of randomisation.

Table 6.3: 1 Patient sets analysed

Class of endpoint	SCR	TS	FAS
Secondary efficacy endpoints			OC, OC-IR, LOCF
Other continuous efficacy endpoints			OC, LOCF
Other binary efficacy endpoints			NCF
Primary safety endpoints		OR	
Other safety endpoints			OR, OC-IR, LOCF-IR
Disposition	OR		
Demographic			OR
Baseline endpoints			OC

OR: Original results, LOCF-IR: Last observation carried forward including values after rescue, OC-IR: Observed case including values after rescue, NCF: Non-completers considered failure

## **6.5 POOLING OF CENTRES**

This section is not applicable because centre is not included in the statistical model.

## **6.6 HANDLING OF MISSING DATA AND OUTLIERS**

Based on the different reasons of patients' data missing for different endpoints, various methods will be used to assess the impact of missing data on efficacy endpoints of this trial, depending upon the type of the endpoint (see [Table 6.3: 1](#)).

### **Original result (OR) analysis**

OR analysis implies the analysis of data exactly as observed, no time windowing as described in [Section 6.7](#). OR analysis will be performed on endpoints that are either not affected by patients' rescue medication use (see [Section 5.4.2](#)) or if it is not meaningful to apply any imputation rule on them for replacing the missing values.

### **Observed cases (OC) analysis**

For all efficacy endpoints, it is planned to analyse only the available data that are observed while patients are on treatment. In other words, missing data will not be replaced in the OC analysis. The time window as described in [Section 6.7](#) is to be considered in the OC approach. For all efficacy endpoints, this OC-technique will set to missing for all values measured after the first day of taking rescue medication (see [Section 5.4.2](#)).

For lipid parameters, it is planned to analyse by using OC- technique but including the original observed values after taking rescue medication. That is called OC including values on rescue medication (OC-IR).

### **Last observation carried forward (LOCF)**

For quantitative endpoints, missing values will be replaced by the last observed measurement on treatment. If the patient has no on-treatment value, baseline value will be carried forward. This method tends to result in more conservative estimates than an OC-analysis. The values measured after taking rescue medication during the treatment period will be set to missing, and these missing values will be imputed by LOCF approach.

The last observation on-treatment need not necessarily to be a value selected as a visit value if multiple measurements are performed within a time window for a visit. In this case the last on-treatment value within time window will be carried forward, while the visit value can be the value that is observed closest to the planned visit date or the first value observed in the time window. See [Section 6.7](#).

Missing values within a course of measurements on treatment will be interpolated based on the last observed value before the missing visit and the first observed value after the missing visit. This is independent from the selection of a value as the picked visit value to be used in the descriptive analysis by visit.

Let:

$D_0$  = date of a visit with a missing endpoint value;

$D_1$  = date of the next-visit (with end-point value non-missing) after the visit with a missing endpoint;

$D_{-1}$  = date of the previous-visit (with end-point value non-missing) before the visit with a missing endpoint;

$E_i$  = endpoint values for visits  $D_{-1}$ ,  $D_0$ ,  $D_1$  for  $i=-1, 0$  and  $1$ )

Then the missing endpoint value can be interpolated as:

$$E_0 = E_{-1} + ((E_1 - E_{-1}) \times (D_0 - D_{-1}) / (D_1 - D_{-1})).$$

For lipid parameters, it is planned to analyse by using LOCF- technique but including the original observed values after taking rescue medication. That called LOCF including values on rescue medication (LOCF-IR).

### **Non-completes considered failure (NCF)**

For binary endpoints, a conservative method to replace missing values is to consider them as “failures”. Missing data due to early discontinuation will be replaced as “failure” up to the planned final visit. The values measured after taking rescue medication will be replaced as “failure”.

For binary endpoints that are derived from quantitative endpoints, missing values within a course of measurements on treatment will be replaced on the basis of the corresponding imputed value of the underlying quantitative endpoint.

### **Safety and other variables**

Missing safety data will not be replaced, but an analysis of the changes from baseline to the last available value under treatment and the minimum and maximum post baseline will be determined for quantitative safety laboratory variables.

### **Missing dates and times**

Missing or partial date information for AEs will be replaced according to general Boehringer Ingelheim (BI) rules described in the BI guidance for “Handling of missing and incomplete AE dates” ([1](#)).

If the date of first drug administration is missing but the patient has been randomised, the date of the first drug administration will be set to the date of randomisation. If the date of first administration is partially missing with the month and year present, the day will be set to the date of randomisation if randomisation is in the same month. If randomisation is in the month prior to the first drug administration, the missing day will be imputed as the first day of the month. A missing time of first drug administration will be imputed as 12:00 o’clock in the morning.

As a general rule, a missing drug stop date will be imputed according to the following principles.

- If an End of treatment (EoT) visit is documented, it should be the date of the EoT visit.
- If the date is incomplete with only month and year and the EoT visit is missing, it should be the first day of the following month.
- If the patient is lost to follow-up, it should be the date of the last visit + 1 or the longest treatment duration based on drug supply + 1 day.
- If the patient dies during the course of the trial and no additional information about drug stop date are available, the date of death will be used as drug stop date assuming that the patient takes the medication until the day of death.
- All other cases need to be assessed by the trial team on an individual basis, trying to use the points above as guidance.

If only the year of birth is known, the day and month of birth will be imputed as 01 January. For other incomplete date information always the midpoint of the possible interval will be used. If only the year is present, the day and month will be imputed as 01 July, if year and month is present, the day will be imputed as 15. If the year is missing, the date will be considered missing.

For partial start and stop dates for concomitant therapies and additional antidiabetic drugs, the following derivations will be used to impute “worst case” values.

- If the day of the end date is missing then end date is set to last day of the month.

- If the day and month of the end date are missing then end date is set to 31st December of the year.
- If the day of the start date is missing then the start date is set to first day of the month.
- If the day and month of the start date are missing then the start date is set to 1st January of the year.
- All other cases need to be assessed by the team on an individual basis, using the above points as guidance.

#### Values below/above limits of quantifications

For biomarkers (insulin, glucagon) we will replace the values which are below the lower limit of quantification (LLQ) with 2/3 times LLQ. This is approximately the median of the expected “true” value if the biomarker follows a normal distribution. We will replace the values which are above the upper limit of quantification (ULQ) with 3/2 times ULQ. With this approach even a change of the method with different limit of quantifications can be handled within a trial. The number of below the LLQ will be included in the biomarker table.

## **6.7 BASELINE, TIME WINDOWS AND CALCULATED VISITS**

With regard to efficacy and safety endpoints, the term “baseline” refers to the last observed measurement prior to administration of any randomised study medication.

Measurements taken prior to the first intake of randomised study medication will be considered pre-treatment values. These pre-treatment values will be assigned to a visit according to the nominal visit number as record on the eCRF or provided by the laboratory.

The date and clock time of the first drug administration will be used to separate pre-treatment from on-treatment values. Measurements taken after the first intake of randomised study drug will be considered on-treatment values if they have been obtained up to end of the parameter specific follow-up period as defined in [Table 6.7: 1](#) below and will be assigned to the randomised study drug for efficacy analyses and to the first study drug taken for safety analyses.

Measurements taken after the end of the endpoint specific follow-up period and after the last intake of study drug will be considered post-treatment values.

**Table 6.7: 1** Endpoint specific follow-up period for the assignment to active treatment

Endpoint	Last day of assignment to treatment phase (days after study drug stop date)
Efficacy	
HbA1c	7
FPG	1
Body weight	1
Blood pressure	1
Insulin and glucagon	1
Waist circumference	7
Safety	
Adverse events	7
Safety laboratory measurements	3
Pulse rate	1

On-treatment efficacy and safety measurements will be assigned to visits based on time windows around the planned visit dates. These time windows are defined based on the planned number of days after the date of first administration of study drug (usually this is at Visit 7).

The midpoint between two on-treatment visits defines the end of a time window, with the midpoint being included in the time window of the preceding visit. The end of the time window of the last on-treatment visit is endpoint dependent (see [Table 6.7: 1](#)).

**Table 6.7: 2** Time windows for on-treatment HbA1c, body weight, and waist circumference measurements scheduled for each on-treatment visit

Visit number	Visit label	Planned days	Time window (actual days on treatment)	
			Start	End A
7	Baseline	0	NA	1 B
9	Week 8	56	2	98
11	Week 20	140	99	196
13	Week 36	252	197	308
15	Week 52/EoT	364	309	Study drug stop date + X days

A In case of premature discontinuation of the study drug a Visit 15 has to be performed. If such a Visit 15 falls into the time window of a previous visit, measurements will be assigned to this previous visit and the visit value will be determined as described below. In this case the time window for the visit that includes Visit 15 will end X days after the study drug stop date, including Day X. The definition of X is endpoint specific, cf. [Table 6.7: 1](#). As visit 16 is optional, no time window for this visit is planned.

B Only values taken prior to the start of treatment with randomised study drug can be considered baseline values. Time windows will be used for assignment of measurements to scheduled visits.

**Table 6.7: 3** Time windows for on-treatment FPG, vital sign, and safety lab measurements scheduled for each on-treatment visit

Visit number	Visit label	Planned days	Time window (actual days on treatment)	
			Start	End A
7	Baseline	0	NA	1 B
8	Week 4	28	2	42
9	Week 8	56	43	70
10	Week 12	84	71	112
11	Week 20	140	113	168
12	Week 28	196	169	224
13	Week 36	252	225	280
14	Week 44	308	281	336
15	Week 52/EoT	364	337	Study drug stop date + X days

A In case of premature discontinuation of the study drug a Visit 15 has to be performed. If such a Visit 15 falls into the time window of a previous visit, measurements will be assigned to this previous visit and the visit value will be determined as described below. In this case the time window for the visit that includes Visit 15 will end X days after the study drug stop date, including Day X. The definition of X is endpoint specific, cf. [Table 6.7: 1](#). As visit 16 is optional, no time window for this visit is planned.

B Only values taken prior to the start of treatment with randomised study drug can be considered baseline values. Time windows will be used for assignment of measurements to scheduled visits.

**Table 6.7: 4** Time windows for on-treatment biomarkers measurement and bone markers scheduled for each on-treatments visit

Visit number	Visit label	Planned days	Time window (actual days on treatment)	
			Start	End A
7	Baseline	0	NA	1 B
15	Week 52/EoT	364	2	Study drug stop date + X days

A In case of premature discontinuation of the study drug a Visit 15 has to be performed. If such a Visit 15 falls into the time window of a previous visit, measurements will be assigned to this previous visit and the visit value will be determined as described below. In this case the time window for the visit that includes Visit 15 will end X days after the study drug stop date, including Day X. The definition of X is endpoint specific, cf. [Table 6.7: 1](#). As visit 16 is optional, no time window for this visit is planned.

B Only values taken prior to the start of treatment with randomised study drug can be considered baseline values. Time windows will be used for assignment of measurements to scheduled visits.

Repeated and unscheduled efficacy and safety measurements will be assigned to the nominal visits and listed in the Clinical Trial Report (CTR) Appendix 16.2 according to the time windows described above. Only one observation per time window will be selected for analysis at an on-treatment visit – the value will be selected which is the closest to the protocol-planned visit day. If there are two observations that have the same difference in days to the planned day or if there are two observations on the same day, the first value will be used. If an observation is available on the last day of treatment, this observation will be preferably selected over any later observation that is still within the time window (not applicable for standard laboratory summaries). If there are multiple values within the time window of the last visit, including a value on the last day of drug intake, the value on the last day of drug intake is used as the value of the last visit.

## **7. PLANNED ANALYSIS**

For End-of-Text tables, the set of summary statistics is: N (number of patients with nonmissing values) / Mean / SD / Min / Q1 / Median / Q3 / Max.

Tabulations of frequencies for categorical data will include all possible categories and will display the number of observations in a category as well as the percentage [%] relative to the respective treatment group. Percentages will be rounded to one decimal place. The category missing will be displayed if and only if there are actually missing values. Percentages will be based on all patients in the respective patient set whether they have non-missing values or not.

Disposition of the patient population participating in the trial will be analysed by treatment groups on the SCR and presented in the CTR as a frequency-distribution. Reason for not randomising screened patients will be tabulated on the SCR.

The frequency of patients in different analysis sets will also be analysed for each treatment group.

### **7.1 DEMOGRAPHIC AND OTHER BASELINE CHARACTERISTICS**

Descriptive analysis of the demographic variables and baseline characteristics described in [Section 5.4.1](#) will be presented on the FAS.

### **7.2 CONCOMITANT DISEASES AND MEDICATION**

Only descriptive statistics are planned for this section of the CTR using the FAS.

CT will be summarised by Anatomical-Therapeutic-Chemical classification level 3 (ATC3) and preferred name at baseline and on-treatment on the FAS. Separate summaries of use of antihypertensives, acetylsalicylic acid (ASA), or lipid lowering drugs at baseline by preferred name will be presented on the FAS.

Antidiabetic medication introduced on treatment will be summarised on the FAS.

Concomitant diseases will be summarised by MedDRA system organ class (SOC) and preferred term (PT) on the FAS. Relevant diabetic medical history will also be presented on the FAS.

### **7.3 TREATMENT COMPLIANCE**

Only descriptive statistics are planned for this section of the CTR. The number and percentage of patients with overall compliance for the study drug will be summarised on the FAS. The overall compliance will be calculated as a weighted average of reported

compliance. The sum of all reported compliance over the planned visits (disregarding run-in) will be divided by the total duration (until last visit where medication is returned).

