4.1.4 Drug assignment and administration of doses for each patient

The treatments to be evaluated are outlined in Table 4.1.4: 1 below. Patients who are qualified will be randomised to one of the dosage and treatment schedules described below. Medication will be dispensed in a double-blind and double-dummy fashion.

All patients will be assigned to a placebo run-in kit at the beginning of the placebo run-in period (Visit 6), and dispensing will be done just once. Dispensing of kits for the double-blind treatment period will begin at Visit 7. Dispensing will be done on 8 occasions over a period of 52 weeks (i.e. every 4 weeks in Visit 7 to Visit 10; every 8 weeks in Visit 11 to Visit 14). Patients will receive empagliflozin as trial medication. However, background medication will not be dispensed as trial medication. Therefore, background medication (liraglutide) will be prescribed at each clinical site. For details regarding packaging (e.g. number of tablets per container), please see Section 4.1.6.

c03122586-03

Proprietary confidential information © 2017 Boehringer Ingelheim International GmbH or one or more of its affiliated companies

Table 4.1.4: 1 Empagliflozin, oral administration per dose group and day

Dose group	Empagliflozin	Empagliflozin	Total units	Timing
	10 mg	25 mg	per dose	
	C	S	1	
Placebo run-in period				
(open label)				
All patients	Matching placebo	Matching placebo	2 tablets	Once daily,
•				Morning
Treatment period				
Empagliflozin	Active drug	Matching placebo	2 tablets	Once daily,
10 mg	S	C 1		Morning
C	M. (1' 1 1	A - 4' 1	2 . 11 .	0 1.1-
Empagliflozin	Matching placebo	Active drug	2 tablets	Once daily,
25 mg				Morning

Placebo run-in period (open label):

From the start of the placebo run-in period, patients should be instructed to take their trial medication once daily with water. The medication should be taken at the same time every day. If a dose is missed by more than 12 hours, that dose should be skipped and the next dose should be taken as scheduled.

Double-blind period:

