4.1.6 Packaging, labelling, and re-supply

Study medication will be provided by BI.

The study medication will consist of containers labelled with the trial identification and medication kit number. Each kit will contain an appropriate number of empagliflozin tablets or matching placebo tablets with some reserve (see below), for dosing until the next scheduled visit.

The placebo run-in kit, assigned to all patients successfully completing Visit 6, will contain 42 tablets in a wallet (i.e., sufficient supply for 2-week administration, with supply for 1-week administration in reserve). One kit type (wallet) will be used for the double-blind treatment either 4 weeks or 8 weeks interval. Wallet will contain 84 tablets (i.e., sufficient supply for 4-week administration, with supply for 2-week administration in reserve). When patients are in the 4 weeks interval at Visits 7, 8, and 9, they will receive one wallet. When patients are in the 8 weeks interval at Visit 10, 11, 12, 13 and 14, they will receive 2 wallets. The total number of tablets dispensed to a patient during the double-blind treatment period will therefore be 1092 at a maximum.

Supply and re-supply will be managed by IRT.

For details of packaging and the description of the label, refer to the ISF.

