4.3 TREATMENT COMPLIANCE

Patients are requested to bring all remaining trial medication including empty package material when attending visits.

Based on tablet counts, treatment compliance will be calculated as the number of tablet taken, divided by the number of tablet which should have been taken according to the scheduled period, multiplied by 100. Compliance will be verified by the on-site monitor authorised by the Sponsor.

Treatment compliance (%) =
$$\frac{\text{Number of tablet actually taken} \times 100}{\text{Number of tablet which should have been taken}}$$

If the treatment compliance is not between 80-120%, site staff will explain the patient the importance of treatment compliance.

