	A3.11	Intake of an investigational drug in another trial within 30 days prior to intake of study medication in this trial	EX16 (Medical judgement), depending on the type of drug given in the prior trial (only if investigational drug interferes with glucose metabolism).	None	Program
	A3.12	Specific exclusion criterion for pre-menopausal women violated	EX14	None	Program
	A3.13	Relevant alcohol or drug abuse and other conditions affecting study compliance	EX15	None	Program
	A3.14	Any other clinical condition unsafe for participation that would jeopardise patient safety while participating in this clinical trial	EX17	None	Program
	A3.15	Liraglutide dose prior to or during placebo run-in period not as required	EX11	None	Program
B		Informed Consent			
	B1	Informed consent not given	Date of informed consent missing, or No signature on patient's "Declaration of Informed Consent"  Patient's data will not be used at all.	All	Program
	B2	Informed consent too late	Date of informed consent not obtained prior to any study related procedure.	None	Program
C		Trial medication and randomisation			
C1		Incorrect trial medication taken			
	C1.01	No study medication taken	Patient randomised but no study medication taken.	TS	Program
	C1.02	Incorrect trial medication taken	Wrong medication taken for more than 20% of the overall treatment duration. Can only be finally judged after DBL since unblinding information is required.	None	Manual
C2		Randomisation not followed			
	C2.01	Treated without randomisation	Patient was treated, but not randomised according to IRT.	None	Program

\*For "Program", ADS will be created by program. For "manual", ADS will be created by important excel spread sheet.

CT: Concomitant therapy, IRT: Interactive response tool, DBL: Data base lock, FAS: Full analysis set, TS: Treated set, eCRF: electronic case report form

Table 6.2: 1 (cont'd) Important PVs

Category / Code		Description	Comment/Example	Exclude from	Program/manual?*
C3		Non-compliance			
	C3.01	Non-compliance with study drug intake	Overall study treatment compliance outside 80% and 120% (exclusive) or study treatment compliance below 80% in the last visit interval.	None	Program
	C3.03	Last treatment more than 7 days prior to next visit	Last treatment more than 7 days prior to next visit.	None	Manual
C4		Medication code broken			

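### Does the SAP's overall-compliance formula score fully compliant patients at about 2% and flag everyone as non-compliant?

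*SAP*

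**What the plan says.** Protocol section 4.3 defines compliance from tablet counts: "treatment compliance will be calculated as the number of tablet taken, divided by the number of tablet which should have been taken" over the scheduled period, times 100. Site staff counsel the patient when the result is not between 80% and 120%.

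SAP section 7.3 turns the visit-level figures into one figure per patient in two sentences. The first names the measure: "The overall compliance will be calculated as a weighted average of reported" compliance. The second describes the calculation: "The sum of all reported compliance over the planned visits (disregarding run-in) will be divided by the total duration", with duration counted to the last visit at which medication is returned. The result is summarised descriptively on the full analysis set.

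The figure has one other use. In SAP Table 6.2: 1, important protocol violation C3.01 is met by "Overall study treatment compliance outside 80% and 120% (exclusive) or study treatment compliance below 80% in the last visit interval". Its entry in the exclusion column is None.

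The dispensing intervals are unequal. Protocol section 4.1.4 states: "Dispensing will be done on 8 occasions over a period of 52 weeks". Section 4.1.6 gives their lengths: "When patients are in the 4 weeks interval at Visits 7, 8, and 9, they will receive one wallet", and "When patients are in the 8 weeks interval at Visit 10, 11, 12, 13 and 14, they will receive 2 wallets".

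**The concern.** Each reported compliance is a percentage. A sum of percentages divided by a duration is a percentage per unit of time, which is not an average and cannot be compared with limits of 80% and 120%. The step that would make it an average, multiplying each percentage by its interval length, is not written down, and neither is the time unit.

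If the sentence were programmed exactly as it stands, the compliance table would be meaningless and C3.01, which the SAP marks as derived by program, would flag every patient. A programmer who noticed the absurd result would have to choose a repair. One obvious repair, the simple mean over visits, is not equivalent to duration weighting because the intervals differ in length.

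**Working it through.** The documents give no numerical compliance result to reproduce, so the check compares readings of the rule.

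**Inputs.** The flow chart places the treatment visits at weeks 0, 4, 8, 12, 20, 28, 36, 44 and 52. That gives eight intervals of 4, 4, 4, 8, 8, 8, 8 and 8 weeks, in line with Protocol sections 4.1.4 and 4.1.6. In days: 3 × 28 + 5 × 56 = 84 + 280 = 364. Write c for an interval's compliance in percent and d for its length in days.

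**Reading 1: the second sentence alone, Σc / T.** For 100% in all eight intervals:
- T in days: 800/364 = 2.2
- T in weeks: 800/52 = 15.4
- T in months: 800/12 = 66.7

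All are below 80. In days, reaching 80 would need a mean interval compliance of 80 × 364/8 = 3,640%. A patient who stopped after one interval with perfect compliance would score 100/28 = 3.6.

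**Reading 2: the two sentences together, Σ(c × d) / Σd.** For 100% throughout: (100 × 364)/364 = 100%. The time unit cancels, so its absence no longer matters.

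**Agreement with the Protocol.** Protocol Table 4.1.4: 1 has every patient taking two tablets daily, so the tablets due in an interval are 2d and the tablets taken are 2d × c/100. Pooled over the treatment period, 100 × taken/due = Σ(c × 2d) / Σ(2d) = Σ(c × d) / Σd. Reading 2 is therefore the Protocol's tablet ratio applied to the whole period.

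**How far a simple mean over visits could stray.** It gives the three 4-week intervals a weight of 3/8 = 37.5%. Duration weighting gives them 84/364 = 23.1%. The two results therefore differ by 14.4% of the gap between mean compliance in the 4-week and the 8-week intervals. A 10-point gap moves the result by 1.4 points. Three constructed patients:

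| Compliance pattern | Simple mean | Duration-weighted |
|---|---|---|
| 100% in six intervals, 60% in the last two | 720/8 = 90.0% | 31,920/364 = 87.7% |
| 100% in three 4-week, 67% in four 8-week, 85% in the last | 653/8 = 81.6% | 28,168/364 = 77.4% |
| 60% in three 4-week, 90% in five 8-week | 630/8 = 78.8% | 30,240/364 = 83.1% |

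The first patient meets C3.01 under either method, because the last interval is below 80%. The second and third change status, in opposite directions. Both need a gap of about 30 points between early and late compliance and an overall value close to 80%.

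**The case for a change.** The best argument for acting is that a SAP exists to give detailed procedures, that C3.01 is derived by program, and that the only arithmetic offered does not work in any natural time unit. The label and the calculation disagree, the intended step has to be inferred, and the table above shows that an unweighted repair can change who is flagged. With 64 randomised patients, 32 per arm, one misclassified patient is 1/64 = 1.6% of the total or 1/32 = 3.1% of an arm. Writing the formula out would take one line.

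Part of this stands. The second sentence is incomplete, duration weighting is the right completion, and a simple mean is not interchangeable with it. What does not stand is the step from an incomplete sentence to a plan that flags every patient. That needs a programmer to disregard the sentence immediately before, which calls the result a weighted average, and then to accept values near 2% against limits of 80% and 120%. An error of that size would be seen in the first test output. The simple mean is a less visible mistake, but it too conflicts with the text: it is not weighted, and its denominator is the number of visits, not the total duration.

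**Conclusion.** The concern does not call for a change. The calculation sentence in SAP section 7.3 omits the interval-length weight, but the sentence before it, the stated denominator and the Protocol's tablet ratio all lead to the same quantity: a duration-weighted average that equals 100% for a fully compliant patient. The figure of 2.2% arises only if that sentence is read in isolation and duration is taken in days.

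Little depends on it in any case. Compliance is reported descriptively, C3.01 excludes no patient from the treated set or the full analysis set, the trial has no confirmatory testing, and neither the frequency of drug-related adverse events nor the HbA1c repeated-measures model uses compliance. The most a plausible misreading could do is alter a descriptive table by a few points and move an occasional borderline patient into or out of the C3.01 count.

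This rests on two assumptions: that analysts read the two sentences together, and that intervals are close to their planned lengths. The second is not critical, since the same identity holds with actual days when the tablets due are counted over those days.
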